##### Secondary outcomes

- The Haemorrhoid Severity Score (HSS) (Annex 3 “Collected variables”) (6), a physician-reported outcome, will be completed by Investigator at baseline and day 30, at the end of the treatment with the MD.

##### safety outcome

- Evaluation of AE, SAE, ADE, SADE, ASADE, USADE incidence assessed by Investigator and reported according to the current legislation for the whole study period. Device Deficiencies (DD) will be also evaluated.

The HS is a physician-reported measurement instrument based on PNR-Bleed classification, that classifies and describes the haemorrhoids based on the four main characteristics of the hemorrhoidal disease i.e., the degree of hemorrhoidal Prolapse (P), Number (N) of the primary hemorrhoidal columns involved, Relation (R) of the haemorrhoidal tissue to the dentate line and the amount of Bleeding (B) from it. All four components in this classification system are graded into five grades ranging from 1 to 5. Grade 1 is the normal anal cushions and Grade 5 is the worst grade in a specific characteristic. HSS is the total score obtained by the sum of the numerical grades of all four characteristics of haemorrhoids in the PNR-Bleed classification. The minimum HSS score is 4 and the maximum score can be 20. The HSS score of a normal person without any signs and symptoms of haemorrhoids is 4. Calculation of the HSS help in the quantification of the haemorrhoidal disease for further reference and is helpful in post-treatment patient follow-up to grade the response to treatment and to assess the effectiveness or failure of any particular treatment regimen for haemorrhoids. It may also be used in predicting and diagnosing the recurrence after any form of treatment for the haemorrhoids.

- The Haemorrhoidal Disease Symptom Score (HDSS) (Annex 3 “Collected variables”) (5,19) is a patient-reported outcome. The questionnaire will be administered by Investigator to each patient at baseline and on day 30, at the end of the treatment with the MD.

The HDSS is a patient-reported measurement instrument. It comprises five items. Symptoms are assessed using the patient-reported frequency of the 5 symptoms, including pain, itching, bleeding, soiling, and prolapse. Patients are instructed to answer based on their experience during the previous period. Each symptom is graded on a 5-point scale (0 = never, 1 = less than once a month, 2 = less than once a week, 3 = 1–6 days per week, 4 = every day or always), giving a total score ranging from 0 to 20.

### **3.6. DEFINITIONS AND PROCEDURE FOR REPORTING OF ADVERSE EVENTS**

#### **3.6.1. DEFINITIONS**

##### **Adverse Event (AE)**

Any untoward medical occurrence, unintended disease or injury or any untoward clinical signs, including an abnormal laboratory finding, in subjects, users or other persons, in the context of a clinical investigation, whether or not related to the Investigational Medical Device (IMD).

- a. This definition includes events that are anticipated as well as unanticipated events.
- b. This definition includes events occurring in the context of a clinical investigation related to the investigational device, the comparator or the procedures involved (for the purpose of safety reporting all activities related to the use of a medical device may be considered procedures).

##### **Serious Adverse Event (SAE)**

Any adverse event that led to any of the following:

- a) death,
- b) serious deterioration in the health of the subject, that resulted in any of the following:
  - i. life-threatening illness or injury,
  - ii. permanent impairment of a body structure or a body function,
  - iii. hospitalization or prolongation of patient hospitalization,
  - iv. medical or surgical intervention to prevent life-threatening illness or injury or permanent impairment to a body structure or a body function,
  - v. chronic disease,
- c) foetal distress, foetal death or a congenital physical or mental impairment or birth defect

##### **Device Deficiency (DD)**

Device deficiency is any inadequacy in the identity, quality, durability, reliability, safety or performance of an investigational device, including malfunction, use errors or inadequacy in the information supplied by the manufacturer.

##### **Incident**

Incident means any malfunction or deterioration in the characteristics or performance of a device made available on the market, including use-error due to ergonomic features, as well as any inadequacy in the information supplied by the manufacturer and any undesirable side-effect.

#### **Serious Incident**

Serious Incident means any incident that directly or indirectly led, might have led or might lead to any of the following: (a) the death of a patient, user or other person, (b) the temporary or permanent serious deterioration of a patient's, user's or other person's state of health, (c) a serious public health threat.

#### **Serious Public Health Threat**

Serious Public Health Threat means an event which could result in imminent risk of death, serious deterioration in a person's state of health, or serious illness, that may require prompt remedial action, and that may cause significant morbidity or mortality in humans, or that is unusual or unexpected for the given place and time.

#### **Corrective Action**

Corrective Action means action taken to eliminate the cause of a potential or actual non-conformity or other undesirable situation.

#### **Field Safety Corrective Action**

Field Safety Corrective Action means corrective action taken by a manufacturer for technical or medical reasons to prevent or reduce the risk of a serious incident in relation to a device made available on the market.

#### **Field Safety Notice**

Field Safety Notice means a communication sent by a manufacturer to users or customers in relation to a field safety corrective action.

#### **User**

User means any healthcare professional or layperson who uses a device.

#### **Adverse Device Effect (ADE)**

Adverse event related to the use of an investigational medical device.

This includes any adverse event resulting from insufficiencies or inadequacies in the instructions for use, the deployment, the implantation, the installation, the operation, or any malfunction of the investigational medical device.

This includes also any event that is a result of a use error or intentional abnormal use of the investigational medical device.

#### **Serious Adverse Device Effect (SADE)**

Adverse device effect that has resulted in any of the consequences characteristics of a serious adverse event.

#### **Unanticipated Serious Adverse Device Effect (USADE)**

Serious adverse device effect which by its nature, incidence, severity or outcome has not been identified in the current version of the risk analysis report.

#### **Anticipated Serious Adverse Device Effect (ASADE)**

Anticipated SADE is an effect that by its nature, incidence, severity or outcome has been previously identified in the risk analysis report.

#### **3.6.2. CLASSIFICATION OF AN ADVERSE EVENT**

The Investigator is responsible for the AE classification, following Annex F of ISO 14155 (reported in Annex 4).

The Investigator is responsible for the following assessment.

##### **1. SEVERITY OF ADVERSE EVENT (AE) ASSESSMENT**

The severity (Intensity) of each AE will be evaluated according to the following 3/point scale: Grade 1, Mild (Events require minimal or no treatment and do not interfere with the participant's daily activities); Grade 2, Moderate (Events result in a low level of inconvenience or concern with the therapeutic measures. Moderate events may cause some interference with functioning); Grade 3, Severe (Events interrupt a participant's usual daily activity and may require systemic drug therapy or other treatment. Severe events are usually incapacitating).

##### **2. CAUSALITY ASSESSMENT**

The Investigator will be responsible for assessing the causal relationship of the AE.

The relationship between the use of the medical device (including the medical-surgical procedure) and the occurrence of each adverse event shall be assessed and categorized.

The investigators (and the Sponsor) will use the following definitions to assess the relationship of the serious adverse event to the investigational device, the comparator or the investigation procedure.

Each SAE will be classified according to four different levels of causality:

1. Not related
2. Possible
3. Probable
4. Causal relationship

The sponsor and the investigators will use the following definitions to assess the relationship of the serious adverse event to the investigational device, the comparator or the investigation procedure:

1. Not related: Relationship to the device, comparator or procedures can be excluded when:

- the event has no temporal relationship with the use of the investigational device, or the procedures related to the application of the investigational device;
- the serious adverse event does not follow a known response pattern to the medical device (if the response pattern is previously known) and is biologically implausible;

- the discontinuation of medical device application or the reduction of the level of activation/exposure - when clinically feasible - and reintroduction of its use (or increase of the level of activation/exposure), do not impact on the serious adverse event;
- the event involves a body-site or an organ that cannot be affected by the device or procedure;
- the serious adverse event can be attributed to another cause (e.g., an underlying or concurrent illness/ clinical condition, an effect of another device, drug, treatment or other risk factors);
- the event does not depend on a false result given by the investigational device used for diagnosis, when applicable;

In order to establish the non-relatedness, not all the criteria listed above might be met at the same time, depending on the type of device/procedures and the serious adverse event.

2. Possible: The relationship with the use of the investigational device or comparator, or the relationship with procedures, is weak but cannot be ruled out completely. Alternative causes are also possible (e.g., an underlying or concurrent illness/ clinical condition or/and an effect of another device, drug or treatment). Cases where relatedness cannot be assessed, or no information has been obtained should also be classified as possible.

3. Probable: The relationship with the use of the investigational device or comparator, or the relationship with procedures, seems relevant and/or the event cannot be reasonably explained by another cause.

4. Causal relationship: the serious adverse event is associated with the investigational device, comparator or with procedures beyond reasonable doubt when:

- the event is a known side effect of the product category the device belongs to or of similar devices and procedures;
- the event has a temporal relationship with investigational device use/application or procedures;
- the event involves a body-site or organ that
  - the investigational device or procedures are applied to;
  - the investigational device or procedures have an effect on;
- the serious adverse event follows a known response pattern to the medical device (if the response pattern is previously known);
- the discontinuation of medical device application (or reduction of the level of activation/exposure) and reintroduction of its use (or increase of the level of activation/exposure), impact on the serious adverse event (when clinically feasible);
- other possible causes (e.g., an underlying or concurrent illness/ clinical condition or/and an effect of another device, drug or treatment) have been adequately ruled out;
- harm to the subject is due to error in use;
- the event depends on a false result given by the investigational device used for diagnosis, when applicable;

In order to establish the relatedness, not all the criteria listed above might be met at the same time, depending on the type of device/procedures and the serious adverse event.

Only causality level 1 (i.e., "not related") is excluded from reporting. If either the sponsor or the investigator has assigned a higher causality level than "not related", the event should be reported.

During causality assessment activity, clinical judgement shall be used and the relevant documents, such as the Investigator's Brochure, the Clinical Investigation Plan or the Risk Analysis Report shall be consulted, as all the foreseeable serious adverse events and the potential risks are listed and assessed there. The presence of confounding factors, such as concomitant medication/treatment, the natural history of the underlying disease, other concurrent illnesses or risk factors shall also be considered.

The above considerations apply also to the serious adverse events occurring in the comparison group.

### **3. TIME PERIOD AND FREQUENCY FOR EVENT ASSESSMENT AND FOLLOW-UP**

The occurrence of an adverse event (AE) or serious adverse event (SAE) may come to the attention of study personnel during study visits and interviews of a study participant presenting for medical care. At each visit/assessment, the participant should be assessed for the possible occurrence of an AE/SAE. Care will be taken not to introduce bias when detecting adverse events and/or SAEs. Open-ended and non-leading verbal questioning of the participant is the preferred method to inquire about adverse event occurrences.

Any medical condition that is present at the time that the participant is screened will be considered a baseline and not reported as an AE. However, if the study participant's condition deteriorates at any time during the study, it will be recorded as an AE. Changes in the severity of an AE will be documented to allow an assessment of the duration of the event at each level of severity to be performed. AEs characterized as intermittent require documentation of the onset and duration of each episode.

AE/SAE can occur during any period of the study. The Investigator will record all reportable events with start dates occurring any time after informed consent is obtained until 7 (for non-serious AEs) or 30 days (for SAEs) after the last day of study participation. At each study visit, the investigator will inquire about the occurrence of AE/SAEs since the last visit. Each patient will receive a phone call from the investigator 30 days after the end of the study to check if there have been AEs. Events will be followed for outcome information until resolution or stabilization.

AE/SAE, as all medical occurrences, should be recorded by the Investigator in the subject's medical records as source data.

Each identified AE is assessed by the Investigator for Seriousness and Causality relationships to the Investigational Medical device or procedure.

All AE/SAE will be recorded on the appropriate case report form (CRF) by the Investigator.

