Discussion	
The findings of this PMCF study confirm that PROCTOeze® PLUS is effective and safe in relieving the symptoms of haemorrhoidal disease and anal irritation. The significant reduction in pain, itching, burning, and swelling highlights the product's efficacy, while the absence of adverse events demonstrates good tolerability.
 
The statistical analyses demonstrate a significant improvement in quality of life and symptom relief.
 
 
• The SHSDH score decreased markedly, indicating enhanced quality of life.
 
• Both the HDSS and HSS scores showed significant reductions, confirming the device's efficacy in alleviating symptom severity.
 
• The significant interaction in the HSS suggests a gender-related difference in response, which may require further study.
 
• Overall, the safety data were reassuring, with no adverse events reported.
 
 
The integrated tables and figures from the statistical analysis clearly support the robustness of these findings.

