Results	
Demographics and Baseline Characteristics
 
 
Number of Patients: 50
 
Gender Distribution 68% female, 32% male
 
Mean Age Approximately 50 years (SD 13.90) with no significant difference between genders (see Table 1 ).
 
 
Outcome Assessments
 
SHSHD
 
 
Baseline: 14.04 (SD 7.79)
 
End-of-Treatment: 7.80 (SD 3.69)
 
Mean Reduction: 6.24 points (P < 0.0001) (See Table 5 and Figure 2 for detailed analysis.)
 
 
HDSS
 
 
Baseline: 10.12 (SD 3.60)
 
End-of-Treatment: 7.20 (SD 2.47)
 
Mean Reduction: 2.92 points (P < 0.0001) (See Table 6 and Figure 3 for detailed analysis.)
 
 
HSS
 
 
Baseline: 8.50 (SD 2.11)
 
End-of-Treatment: 6.48 (SD 2.17)
 
Mean Reduction: 2.02 points (P < 0.0001)
 
A significant Visit x Gender interaction was found (P = 0.0272). (See Table 7 and Figure 4 for detailed analysis.)
 
 
Device Usage
 
Patient diaries indicated a mean usage of approximately 34 cream applications over the 14-day monitoring period, with daily consumption remaining relatively consistent and a slight decrease observed in the later study days.
 
Safety
 
No serious adverse events (SAEs) were reported. No, AE was reported.
										
Conclusions	
This post-marketing clinical investigation demonstrates that PROCTOeze® PLUS is effective in improving quality of life and reducing the symptoms associated with hemorrhoidal disease and anal irritation in adult patients with Grade I-II hemorrhoids.
 
The significant reductions in SHSHD, HDSS, and HSS scores (all P < 0.0001), combined with an acceptable safety profile, support the continued clinical use of PROCTOeze® PLUS.
 
Ongoing post-marketing surveillance is recommended to further confirm the long-term safety of the device.
										

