### Demographic Dataset

In this study have been enrolled 50 patients (34 - 68.0% - females and 16 - 32.0% males, Table 1).

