**Table 6**

**HDSS: Table 6 - Descriptive statistics**  
**Total of HDSS - V1, V2 and difference V1-V2**

Label	Mean	Std Dev	Minimum	Lower Quartile	Median	Upper Quartile	Maximum	Lower 95% CL for Mean	Upper 95% CL for Mean
Total HDSS V1	10.12	3.60	5.00	8.00	9.00	13.00	19.00	9.10	11.14
Total HDSS V2	7.20	2.47	5.00	5.00	7.00	8.00	16.00	6.50	7.90
DIFF Total HDSS V_1 - V_2	2.92	2.51	-2.00	1.00	2.00	5.00	9.00	2.21	3.63

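### At least one patient's HDSS total rose by 2 points, and the report concludes tolerability from zero AEs without reconciling this with the protocol's rule that deterioration is recorded as an AE

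*Combined protocol and SAP*

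**What the plan says.** **The rule.** Protocol section 3.6.2, item 3 (time period and frequency for event assessment) first sets the baseline: "Any medical condition that is present at the time that the participant is screened will be considered a baseline and not reported as an AE". The next sentence qualifies it: "However, if the study participant's condition deteriorates at any time during the study, it will be recorded as an AE". No minimum change is given, no scale is named, and the study disease is not exempted. The inclusion criteria (section 3.3.1) require symptomatic Grade I-II haemorrhoids, so the study disease is a screening condition in every patient.

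**The data.** In section 9, Statistical Analysis, the Table 6 row "DIFF Total HDSS V_1 - V_2" has mean 2.92, SD 2.51 and minimum -2.00. The text under HDSS confirms that the difference is Visit 1 minus Visit 2. The HDSS adds five symptom-frequency items, and a higher total means more frequent symptoms.

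**The conclusion.** The Safety paragraph of the Summary's Results says "No, AE was reported". The Discussion says "Overall, the safety data were reassuring, with no adverse events reported" and that "the absence of adverse events demonstrates good tolerability".

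**The concern.** The safety conclusion rests on a count of zero. The protocol has a rule under which worsening of the treated disease could enter that count, and an efficacy table in the same report shows worsening on one scale in at least one patient. The report does not say how the rule was applied to the study disease, and does not mention the patient or patients concerned. A reader therefore cannot tell whether the zero means that each rise was examined and judged not to be a deterioration, or that nobody compared the HDSS with the AE record.

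For a topical haemorrhoid product, worsening of the haemorrhoidal symptoms is among the most relevant adverse outcomes. AE incidence is a listed endpoint, and the Summary's Conclusions use the safety profile to support continued clinical use.

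**Working it through.** **Inputs**
- Number of patients, Demographic Dataset: "In this study have been enrolled 50 patients".
- HDSS change, Table 6: mean 2.92, SD 2.51, minimum -2, quartiles 1 and 5, median 2, maximum 9.
- HDSS tests, Table 6.1: t = 8.213142, signed rank S = 479.
- SHSHD change, Tables 5 and 5.1: minimum 0.00, S = 540.5.
- HSS change, Tables 7 and 7.1: minimum 0.00, S = 517.5.

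**Step 1. Reproduce the report's t value.**
t = mean / (SD/√50) = 2.92 / (2.51/√50) = 8.226. Rounding of the SD allows 8.210 to 8.243, so the printed 8.213142 is consistent. Working back, SD = 2.92 × √50 / 8.213142 = 2.51396. The sum of the differences is 50 × 2.92 = 146. The sum of squares is 49 × 2.51396² + 50 × 2.92² = 309.68 + 426.32 = 736.00, an integer, as it must be for integer scores.

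**Step 2. Is the minimum of -2.00 a misprint?**
Assume the usual centred signed-rank statistic with zero differences dropped: S = n'(n'+1)/4 − T⁻. Here n' is the number of non-zero differences and T⁻ is the rank sum of the patients who worsened. If nobody worsened, T⁻ = 0 and S = n'(n'+1)/4.
- HDSS: n' = 43 gives 43 × 44/4 = 473, and n' = 44 gives 44 × 45/4 = 495. No integer n' gives 479, so T⁻ must exceed 0. The smallest case is n' = 44 with T⁻ = 495 − 479 = 16.
- SHSHD: 46 × 47/4 = 540.5 exactly, which fits T⁻ = 0 and the minimum of 0.
- HSS: 45 × 46/4 = 517.5 exactly, which fits T⁻ = 0 and the minimum of 0.

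The exact fit on the other two scales supports the assumed form of S. Table 6.1 thus independently confirms that some HDSS totals rose.

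**Step 3. How many patients?**
I enumerated sets of 50 integer HDSS differences with sum 146, sum of squares 736, minimum -2, maximum 9, 13th ordered value 1, median 2, 38th ordered value 5 and S = 479 (mid-ranks for ties). The feasible numbers at (-2, -1) are (1, 0), (2, 1), (1, 3) and (2, 3), that is 1, 3, 4 or 5 patients, or 2% to 10% of 50.

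One solution can be checked by hand: one patient at -2, six at 0, six at 1, eighteen at 2, five at 4, ten at 5, four at 9.
- Count: 1 + 6 + 6 + 18 + 5 + 10 + 4 = 50.
- Sum: −2 + 6 + 36 + 20 + 50 + 36 = 146.
- Squares: 4 + 6 + 72 + 80 + 250 + 324 = 736.
- T⁻: the 19 patients with an absolute difference of 2 share ranks 7 to 25, so the mid-rank is 16 and T⁻ = 16.

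**Step 4. What one reclassified event would do (exact Clopper-Pearson 95% interval).**
- 0/50: upper limit 1 − 0.025^(1/50) = 7.1%.
- 1/50 = 2.0%: 0.05% to 10.6%.

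Step 4 is conditional. It describes the AE rate only if one HDSS rise is classed as an AE.

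The observed HDSS minimum is 5 at both visits on a scale that starts at 0, which may mean that items were scored 1 to 5. A constant shift cancels in the difference and changes nothing above.

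**The case against.** A reader might infer that the zero-AE statement is contradicted by the report's own table, or that the true AE rate is at least 1/50. The documents do not support either, for these reasons.

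- Nothing links an HDSS rise to deterioration of the participant's condition. AE classification is left to the investigator, the AE definition asks for an untoward medical event, and the preferred way of finding AEs is open questioning. If each rise was judged not to be a deterioration, zero AEs and a minimum of -2.00 are compatible.
- The adjacent tables point the benign way. The minimum change is 0.00 on the SHSHD total and on the investigator-rated HSS total, so nobody's total worsened on either.
- A 2-point rise is weak evidence. It needs only two items to move one category, or one item to move two. The recall period is undefined, and one response category is less than once a month, while the schedule puts Visit 2 at day 14 ± 2. The documents give no reliability or important-change figure.
- The decisions may be documented. Item 3 sends them to medical records and CRFs, and only a blank CRF is shown.

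All of this stands, and it limits the point to an unreconciled conflict. It does not remove the point. The rule has no threshold, the HDSS is completed at Visit 2, where AEs are also assessed, and the report draws a positive conclusion from the zero without mentioning the rises.

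It is also tempting to query every patient with a rise on any single HDSS or HSS item. The rule gives no basis for that, it would catch one-category shifts in patients whose totals improved, and the workload cannot be judged from the published totals.

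**Conclusion.** The point holds as a failure to reconcile three statements: the deterioration rule, a minimum HDSS change of -2.00, and a tolerability conclusion drawn from no AEs. That at least one patient's HDSS total rose by 2 points is certain from Table 6 and is confirmed by Table 6.1. The range of 1 to 5 patients rests on zeros dropped, mid-ranks for ties, and quartiles taken as the 13th and 38th ordered values.

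Whether any rise was an AE is open. If one was, the upper 95% limit for the AE rate moves from 7.1% to 10.6%. The primary endpoint, the power and the efficacy tests are unaffected. The point bears on the safety statement alone, and should be settled before that statement is relied on.

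**What to change.** 1. List the patients whose HDSS total rose from Visit 1 to Visit 2. Totals are enough.
2. For each, have the investigator reconcile the rise with section 3.6.2, item 3: either recorded as an AE with severity and causality, or a documented reason why it is not one. If that decision is already in the CRF or source records, cite it.
3. In the Summary's Results, report the number of patients whose HDSS total worsened next to the reconciled AE count, both out of 50. Quote 1/50 (0.05% to 10.6%) only if one rise is in fact classed as an AE.
4. Reword the tolerability statements in the Summary's Results and Discussion so that they rest on the reconciled count, and say how the rule was applied to the study disease.

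The cost is one listing from data already held, a few queries (1 to 5 patients under the conventions above) and some changed sentences. The downside is that the AE count may become less favourable.
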